Official Study Title: Detecting Neonatal Hypoglycemia Using Real-Time Continuous Glucose Monitoring (CGM)

NCT Number: NCT03032523

Date of Document: 3/6/2019

PROTOCOL

TITLE

Detecting Neonatal Hypoglycemia using Real-Time Continuous Glucose Monitoring (CGM)

SUMMARY

Newborn infants have many complex physiological changes taking place that are difficult to anticipate. Infants born to mothers who have diabetes during their pregnancy are especially vulnerable to hypoglycemia. Our study will evaluate blood sugar changes during the first few days of life and the utility of CGM systems to detect clinically significant hypoglycemia in infants. This randomized, controlled single-blind trial will compare infants on CGM alone versus those using CGM who are remotely monitored by a physician through the Dexcom Share application. The number of hypoglycemic events that are detected in each group will be compared. For each time point that the unblinded CGM group has a low blood sugar level, it will be verified by standard heelstick (capillary) measures. Finally, the sensitivity and specificity of detecting hypoglycemia in the infant will also be determined.

INCLUSION CRITERIA

- Participants must be born at 34 weeks gestation or later
- Participants must be admitted Lucile Packard Children's Hospital
- Infants born at outside hospitals and transferred to LPCH will be eligible for the study
- Mothers have a diagnosis of pre-gestational diabetes
- Mothers with gestational diabetes have poorly controlled gestational diabetes defined as elevated Hemoglobin A1c (greater than 6%) during pregnancy or hyperglycemia based on home glucometer readings while pregnant. This includes fasting or pre-prandial blood glucose values of greater than 100 mg/dl, post-prandial blood glucose values greater than 140mg/dl at 1 hour or greater than 120mg/dl at 2 hours consistently.
- Any mothers who require insulin, metformin, or glucose lowering medications during gestation

EXCLUSION CRITERIA

- Infants <2,000g will be excluded from the study.
- If infants receive Acetaminophen, sensor readings will not be included in the analysis for 6 hours after the medication is given because this medication may falsely raise the sensor's glucose readings.
- Infants will also be excluded if they have an anomaly of the skin or subcutaneous tissue that would prevent proper adhesion, placement, and function of the sensor.

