 - Using the Dexcom Follow Application, auditory and vibratory alerts will be enabled for blood glucose values <46 mg/dl or signal loss for >60 minutes and sent directly to the study physician remotely monitoring participants.
 - Signal loss of greater than 3 hours will require participants to have a new subcutaneous sensor inserted and the initial calibration steps will need to be repeated.
- Dexcom Receivers and Ipods will remain connected to a power source as much as possible during the study period.

DEXCOM CGM PROTOCOL: Calibration

- After the initial 2 hour start-up period, the sensor will be calibrated using two successive capillary blood glucose measurements using a study glucometer.
- The same type of device will be used for all capillary blood glucose measurements performed on the infant.
- For each capillary blood glucose sample, an area of skin will be cleansed, allowed to dry, pricked using a sterile lancet, and the smallest amount of blood possible will be used for proper testing.
- Every effort will be made to ensure capillary blood glucose levels are checked at least every 12 hours from the time of initial calibration until the time of discharge or 7 days of life, whichever comes first.
- Glucose levels will be entered into the transmitter for calibration within 5 minutes of obtaining the glucose measurement.
- In the remote monitoring group, a trained study staff member will work with nursing staff to perform and input the calibration measurements into the receiver.

MONITORING FOR HYPOGLYCEMIA

- When the monitoring physician receives an alert for a low glucose value <46 mg/dl, they will contact the nurse taking care of the patient. First, the infant will be assessed to see if excess pressure is being placed on the sensor due to positioning. If so, the infant may be repositioned and monitored to see if the glucose values rise above 45mg/dl. If CGM glucose values remain low, a bedside glucose reading will be performed. This value will be recorded in the chart and by the monitoring physician in the study. Based on the standard of care blood glucose reading, the staff will take appropriate measures based on the standard of care (see appendix).
- If the hypoglycemia alarm continues for an additional 60 minutes, the nurse caring for the patient will be prompted to obtain an additional standard of care blood glucose measurement.

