- If the measurement at 60 minutes shows that the patient has a BG >45mg/dl, the CGM may be re-calibrated (see below).
- In the case of severe hypoglycemia (BG <35mg/dl) found in both control and experimental groups during routine calibration procedures will require that the clinical staff caring for the patient be notified to ensure safety of the patient.
- For all blood glucose measurements that are >20% different from the Dexcom CGM values in the experimental group, a blood glucose test may be performed to re-calibrate the sensor prior to the 12 hours. Sensor re-calibration will only occur between glucose values of 40 mg/dl and 400 mg/dl based on manufacturer guidelines.

MONITORING FOR SENSOR SITES FOR INFECTION

- Sensor sites will be assessed at least once per 12 hour nursing shift and as needed during nursing cares for the duration of the study.
- Evidence of inflammation (redness, swelling, discharge) will be documented and discussed with the clinical care and research team.
- If the sensor site is thought to be infected, the sensor will be removed immediately and appropriate steps will be taken to treat the infection by the clinical team managing the patient.

RISKS ASSOCIATED WITH CGM USE

When the needle and sensor are inserted, the child should expect to experience a small amount of pain for a few seconds. After insertion, your child may or may not feel some tenderness or pain.

Pain, inflammation or redness, swelling, minor infection, and minor bleeding at the sensor insertion site are possible risks with your child's use of the study device. In extremely rare cases an infection might spread to other parts of the body. Significant or serious health risks with the investigational device are not anticipated.

Minor irritation may occur where the adhesive pad is placed. This will occur in most research participants and should clear up within hours to not more than a week after removal. The child may experience some itching in the area during the healing process, which is normal. The child may develop an allergic reaction to one or more parts of the sensor and transmitter. This is similar to allergies that occur due to medical tape or jewelry. Allergic reactions will usually be mild and require only a skin cream to make them better. Severe allergic reactions are rare. If the child has an allergic reaction, study staff should be notified.

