Hypoglycemia was defined as a glucose concentration of <45mg/dL in order to correspond with the hospital's SOC protocol. Primary outcome measures were the number of hypoglycemic events detected by the sensor that were not detected by the hospital SOC. Secondary outcome measures were sensitivity, specificity, and positive predictive value of the device to detect hypoglycemia. When evaluating number of hypoglycemic episodes that occurred with each infant, the start of each hypoglycemic episode needed to be at least 60 minutes from the last episode to allow for treatment and resolution of hypoglycemia. A duration of 60 minutes was used to allow time for breast feeding in accordance with the nursery's SOC procedures (Supplementary Fig. S1). The CGM data were reviewed post hoc using Dexcom Studio Software. Using the Dexcom Studio Software to calculate the average CGM glucose level for each infant, a value of 39 mg/dL was used for all values that were reported as "low." All values reported by the CGM as "low" were excluded from the accuracy analysis. The mean absolute relative difference (MARD) was calculated by taking the absolute value of the difference between the CGM and hospital glucometer values and dividing by the hospital glucometer value individually, and then taking the mean of these values.

Additional outcome measures included CGM feasibility in the hospital setting. During the recruitment process and throughout the study, we asked caregivers for feedback about satisfaction with the CGM device. If any devices were removed before the end of the study period, we requested feedback from the families as well.

DATA COLLECTION SCHEDULE

Measurement	Study Entry	Daily	End of Study
Demographics	X		
Medical History (mother)	X		X
Medical History (infant)	X		X
Chart Review		X	X
Adverse Events		X	X
Nutrition		X	X
Glycemic Trends		X	X
Exam of skin site/sensor site	X	X	X

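### No rule says which sensor-blood pairs enter sensitivity, specificity and PPV; using all of them would raise sensitivity and lower specificity, because remote-arm alerts trigger extra blood tests

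*Combined protocol and SAP*

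**What the plan says.** Under Data Analysis, Outcome measures: "Secondary outcome measures were sensitivity, specificity, and positive predictive value of the device to detect hypoglycemia". The section defines hypoglycemia as below 45 mg/dL, gives a 60-minute rule for separating episodes, and gives a formula for MARD against the hospital glucometer. Just before that formula it says: "All values reported by the CGM as 'low' were excluded from the accuracy analysis". It also says: "The CGM data were reviewed post hoc using Dexcom Studio Software". The Power calculation section makes the false-positive rate of CGM alerts a goal of the modified study.

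Blood values arise in several ways:

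- **Scheduled.** Calibration checks at least every 12 hours (Dexcom CGM Protocol: Calibration), with a study glucometer. Routine standard-of-care (SOC) tests come on top.
- **Alert-triggered, remote arm only.** After an alert below 46 mg/dL the nurse first checks for pressure on the sensor: "If so, the infant may be repositioned and monitored to see if the glucose values rise above 45mg/dl". Then: "If CGM glucose values remain low, a bedside glucose reading will be performed". If the alarm lasts another 60 minutes, a further blood test is prompted (Monitoring for Hypoglycemia).
- **Discrepancy-triggered, experimental group only.** For "measurements that are >20% different from the Dexcom CGM values in the experimental group, a blood glucose test may be performed" (same section).

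The Summary describes verification more broadly: "For each time point that the unblinded CGM group has a low blood sugar level, it will be verified by standard heelstick (capillary) measures".

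**The concern.** Sensitivity and specificity need sensor-positive and sensor-negative times to be checked against blood in a way that does not depend on the sensor. Here, in one arm, a low sensor reading itself causes a blood test, and a normal reading does not. An analyst who takes every available pair, which the plan permits, over-represents sensor-positive times. This is partial verification bias.

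PPV and the alert false-positive rate are exposed by other routes. A 60-minute repeat counts one alarm twice. An alert cleared by repositioning may never get a blood value. If the 'low' exclusion reached the classification measures, it would drop the clearest sensor-positives, since a 'low' reading is set to 39 mg/dL for averaging, well under the 45 mg/dL cut-off. At stake are the three secondary outcomes and the alert false-positive rate.

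**Working it through.** **Is there a pair rule anywhere?** Three filters exist: sensor readings within 6 hours of acetaminophen, CGM data continued after 7 days, and 'low' readings in the accuracy analysis. None selects pairs by why the blood test was done. For the three measures the plan also leaves open the time window, the reference meter, the unit (reading, episode or infant), pooling of arms, and the sensor cut-off. The alert fires below 46 while the definition is below 45, so a reading of 45 raises an alert without meeting the definition.

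**Direction.** Let routine pairs give TP, FN, FP, TN. Alert tests are done while the sensor is still low, so they add *a* true and *b* false positives and no negatives:

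- sensitivity = (TP + *a*)/(TP + FN + *a*), which rises with *a*;
- specificity = TN/(TN + FP + *b*), which falls with *b*.

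This is algebra. It does not depend on the inputs below.

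**Size, all inputs assumed.** Take 160 routine pairs, 10% truly low, sensitivity 0.60, specificity 0.90: TP = 9.6, FN = 6.4, FP = 14.4, TN = 129.6. Add A alert-triggered pairs, 40% truly low (the same PPV).

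| A | Sensitivity | Specificity | PPV |
|---|---|---|---|
| 0 | 9.6/16 = 0.60 | 129.6/144 = 0.90 | 9.6/24 = 0.40 |
| 20 | 17.6/24 = 0.73 | 129.6/156 = 0.83 | 17.6/44 = 0.40 |
| 40 | 25.6/32 = 0.80 | 129.6/168 = 0.77 | 25.6/64 = 0.40 |
| 60 | 33.6/40 = 0.84 | 129.6/180 = 0.72 | 33.6/84 = 0.40 |

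Other assumed inputs show the same pattern. Take 1,000 times, 10% low, sensitivity 0.70, specificity 0.90 (TP 70, FN 30, FP 90, TN 810), with all sensor-positives but only 25% of sensor-negatives tested. Sensitivity reads 70/77.5 = 0.90 and specificity 202.5/292.5 = 0.69.

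**PPV and repeats.** The constant PPV in the table holds only because the added pairs were given the same PPV. Suppose 40 first alert tests, 16 low and 24 not (0.40), and repeats that agree with the first test. If 20% of true and 50% of false alarms are repeated, PPV per test is (16 + 3.2)/(40 + 3.2 + 12) = 0.35. With the shares reversed it is (16 + 8)/(40 + 8 + 4.8) = 0.45.

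**PPV and untested alerts.** With shares *r* of false and *t* of true alerts untested, observed PPV = 0.4(1 − *t*)/[0.4(1 − *t*) + 0.6(1 − *r*)]. For *t* = 0 it is 0.455 at *r* = 0.2 and 0.625 at *r* = 0.6. For *t* = *r* it stays 0.40.

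**'Low' readings, broad reading only.** On the routine pairs:

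- dropping 20% of true and 50% of false positives gives sensitivity 7.68/14.08 = 0.55, specificity 129.6/136.8 = 0.95 and PPV 7.68/14.88 = 0.52;
- the reverse gives 4.8/11.2 = 0.43, 129.6/141.12 = 0.92 and 4.8/16.32 = 0.29.

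Sensitivity falls and specificity rises, opposite to the pooling effect. PPV can move either way.

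**Discrepancy tests.** These are selected on sensor error, so their effect depends on the direction of the error and is left open.

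**The case against.** The best case against has four parts.

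1. **Nothing says triggered pairs are pooled, and the size is unknowable.** True. It depends on the ratio of triggered to routine tests, and the readable text gives neither alert counts nor the SOC screening schedule. If routine tests are frequent, 20 to 60 triggered per 160 is too many. The size stays open. The direction under the all-pairs choice does not, and the plan does not rule that choice out.

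2. **The 'low' exclusion means MARD only.** Probably so: it stands directly before the MARD definition, and a non-numeric value cannot enter a relative difference. A reader might infer that 'low' readings were dropped from sensitivity, specificity and PPV. The documents do not support that. They only leave the term undefined, and one sentence would settle it.

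3. **The Summary and the monitoring section do not truly conflict.** One summarises and the other is the working procedure. A reader might infer a flat contradiction, but a difference in wording is nearer the mark. It still matters for analysis, because on one wording every low reading has a blood value and on the other some do not.

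4. **The measures are secondary and descriptive, and the data are few.** This bears on how the fix should look. With the assumed 16 true lows split evenly, 8 per arm at sensitivity 0.60 gives a Wilson 95% interval of about 0.29 to 0.85, before clustering. That contains the whole illustrated bias, so separate estimates by arm could be descriptive only.

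A reader might also infer from the constant PPV column that PPV is safe under pooling. It is not, once 60-minute repeats are included.

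**Conclusion.** The point holds. The plan names three accuracy measures without a pair rule, while its own procedures add sensor-triggered blood tests in one arm. Using all pairs unweighted pushes sensitivity up and specificity down. With the assumed inputs the shift is 0.13 to 0.24 in sensitivity and 0.07 to 0.18 in specificity. These figures are illustrations; the documents supply no pair or alert counts.

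For PPV and the alert false-positive rate the conclusion is weaker. First alert tests need not bias them, repeats and untested alerts can, and the direction is not fixed. The 'low' exclusion is a matter for clarification. Nothing here shows an effect on the primary outcome, or that any reported result is wrong by a known amount. The plan should be changed on this point, but it is not critical to the trial's main question.

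**What to change.** 1. **Sensitivity and specificity.** Report them with both arms pooled, and by arm only descriptively, from blood values not triggered by the sensor: 12-hourly checks and routine SOC tests. Pair each with the last CGM reading before the blood sample, within a stated maximum time gap. Name the reference meter: the calibration section uses a study glucometer and the MARD sentence a hospital glucometer. The calibration section does ask for one type of device throughout, but the plan should say whether both sources count. As sensitivity analyses, show the all-pairs estimate and one that keeps triggered tests that replaced a due 12-hourly check.
2. **'Low' readings.** State that they count as sensor-positive for sensitivity, specificity and PPV and are excluded from MARD only.
3. **PPV and the alert false-positive rate (1 minus PPV).** Estimate per remote-arm alert episode, grouped by the 60-minute rule and classified by the first blood test. Bound untested episodes as all false, then all true.
4. **Cut-off and precision.** State whether sensor-positive means below 45 or below 46, and give pair counts and intervals that allow for clustering within infant.
5. **Verification wording.** Reconcile the Summary with Monitoring for Hypoglycemia, so that the denominator of tested alerts is defined.

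**Cost.** No new data are needed. The reason for each test can be tagged afterwards from the stored CGM traces and the monitoring record: "This value will be recorded in the chart and by the monitoring physician in the study". There will be fewer pairs, and intervals will be wide given recruitment below 40 infants. If triggered tests displaced due checks, estimate 1 leans down: with 20% or 60% of sensor-positive checks displaced, the assumed 0.60 becomes 7.68/14.08 = 0.55 or 3.84/10.24 = 0.38. Hence the second sensitivity analysis. PPV bounds may also be wide: with 40 assumed alerts, 16 true, and 20% to 60% of the 24 false ones untested, the lower bound is 16/40 = 0.40 and the upper 20.8/40 = 0.52 to 30.4/40 = 0.76.

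### The sensor-episode rule sets no minimum run below 45 mg/dL, so nothing stops one isolated reading from counting in the primary outcome, mostly as a low missed by SOC

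*Combined protocol and SAP*

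**What the plan says.** The primary outcome, under Outcome measures in DATA ANALYSIS, is a count: "Primary outcome measures were the number of hypoglycemic events detected by the sensor that were not detected by the hospital SOC". Two statements turn a trace into events. The first is a threshold: "Hypoglycemia was defined as a glucose concentration of <45mg/dL". The second is a separation rule: "the start of each hypoglycemic episode needed to be at least 60 minutes from the last episode". The next sentence, "A duration of 60 minutes was used to allow time for breast feeding", explains the length of that gap; it does not say how long a low must last. On how the traces were handled, the section says "The CGM data were reviewed post hoc using Dexcom Studio Software". It also gives a value to use for readings displayed as 'low' when averaging, and leaves those readings out of the accuracy analysis. It does not say how they enter the episode count.

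The bedside procedure is under MONITORING FOR HYPOGLYCEMIA. The alert settings are "auditory and vibratory alerts will be enabled for blood glucose values <46 mg/dl", and each low alert leads to a call to the nurse and a check for pressure on the sensor. If pressure is found: "If so, the infant may be repositioned and monitored to see if the glucose values rise above 45mg/dl". Then: "If CGM glucose values remain low, a bedside glucose reading will be performed". The SUMMARY says something different: every low time point in the unblinded group is to be verified by heelstick, with no condition that the low persists.

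**The concern.** A continuous trace yields many readings, each with error. If a single reading below 45 mg/dL is enough, an infant whose true glucose stays in the 50s will produce events from sensor error alone. The comparator is an occasional spot test, so a short dip will seldom coincide with one and falls into the missed-by-SOC count almost by construction. The revised goal, stated under Power calculation, is to show the additional benefit of CGM in finding lows that SOC misses, so this error pushes the headline result in the favourable direction.

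The definition also leaves room for discretion. Two analysts working from the same traces could reach different primary counts without either departing from the text.

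**Working it through.** **1. Text check.** The documents give no required number of consecutive readings, no minimum time below threshold, no end-of-episode rule, and no statement of whether the 60 minutes runs from the start or the end of the prior episode. Blood confirmation is not a condition for counting a sensor event. A trace reading 52, 44, 52 therefore meets both stated conditions. That one reading suffices follows from applying the rule as written; the text does not say so outright.

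**2. No planned figure to reproduce.** The only design figure is the sample size of 40 for 57% against 32%. It does not bear on how events are counted.

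**3. Assumptions for an illustration (none is in the documents).** One reading every 5 minutes, so 24 × 60 / 5 = 288 per day. True glucose *g* is constant and above 45. Reading = *g* × (1 + SD × *e*), with *e* = √(1 − *w*) × slow drift (autoregressive, 60-minute time constant) + √*w* × white noise, where *w* is the white-noise share of the error variance. Episode starts are at least 60 minutes apart.

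**4. Closed-form check.** Expected false readings per day = 288 × Φ((45 − *g*) / (SD × *g*)), whatever *w* is. This is a ceiling on the one-reading event count.
- *g* = 55, SD 10%: Φ(−10/5.5) = Φ(−1.82) = 0.0345; 288 × 0.0345 = 9.9.
- *g* = 70, SD 10%: Φ(−25/7) = Φ(−3.57) = 0.00018; 288 × 0.00018 = 0.05.

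**5. Simulated false events per infant-day.**

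| True glucose | SD | White share *w* | One reading | Three consecutive |
|---|---|---|---|---|
| 52 | 10% | 50% | 9.1 | 1.3 |
| 55 | 10% | 50% | 4.8 | 0.3 |
| 55 | 10% | 20% | 3.4 | 0.66 |
| 55 | 10% | 10% | 3.0 | 0.90 |
| 55 | 10% | 0% | 2.3 | 1.05 |
| 60 | 10% | 50% | 1.3 | 0.02 |
| 60 | 10% | 0% | 0.57 | 0.19 |
| 65 | 10% | 50% | 0.24 | 0.00 |
| 70 | 10% | 50% | 0.04 | 0.00 |
| 55 | 8% | 50% | 2.1 | 0.06 |
| 55 | 14% | 50% | 9.6 | 1.5 |

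At glucose 55 and SD 10%, the ratio of the two rules falls from 4.8/0.3 = 16 to 2.3/1.05 = 2.2 as the white-noise share goes from half to none. The ratio depends on an error structure that the documents do not describe.

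**6. Second model.** Over 48 hours, with the gap counted from the end of the last low and lag-1 autocorrelation 0.9, glucose 55 and SD 10% give 4.63 events under one reading and 2.06 under three. Per day that is 4.63/2 = 2.3 and 2.06/2 = 1.03, in line with the all-drift row. The one-reading count exceeded the three-reading count in every scenario of both models at glucose 52 to 65. At 70 both are small when SD is 10%, but at SD 15% the second model still gives 1.6 to 4.7 versus 0 to 0.5 per 48 hours.

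**The case against.** A reader might infer that the plan states a one-reading rule. It does not. It is silent, and an analyst using Dexcom Studio may have applied an unwritten minimum. This stands as a limit on the wording, but the only written rule admits a single reading.

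A reader might also infer that the bedside procedure disregards brief lows and so contradicts the outcome definition. The documents do not support that. The alert needs no persistence, every low alert brings a nurse contact and an assessment, and the watch-and-wait step is tied to pressure on the sensor. What can be said is that a low that does not persist gets no bedside glucose under MONITORING FOR HYPOGLYCEMIA, while the SUMMARY promises verification of every low time point. Those two passages conflict with each other and must be reconciled.

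Positive predictive value, specificity and the false-positive rate of alerts are all planned, so sensor noise will be partly visible. They do not correct the primary count, because a dip with no paired blood value cannot enter them.

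The large ratios are easy to over-read. They need true glucose near the threshold and substantial reading-to-reading noise; this objection stands in full. So does the point that three readings has no basis in the documents, and that choosing a rule after the traces were reviewed makes the definition data-dependent unless this is disclosed.

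**Conclusion.** The point holds as a gap in the primary-outcome definition. Isolated sensor readings below 45 mg/dL can count as events, and with intermittent SOC testing most are scored as missed by SOC, in favour of CGM. The direction was the same wherever the simulations gave appreciable counts. The size in this trial is unknown: the range of 4.8 versus 0.3 to 2.3 versus 1.05 false events per infant-day is illustrative and rests on an assumed 5-minute interval, 10% error SD and constant true glucose of 55. With that error SD the effect all but vanishes at glucose 70. The claim that the bedside pathway and the outcome rule are opposites should not be made. This is a worthwhile, inexpensive improvement and does not by itself invalidate the trial.

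**What to change.** In Outcome measures, define a sensor episode as a stated minimum run below 45 mg/dL, for example at least three consecutive readings (about 15 minutes at the assumed interval). State that a displayed 'low' counts as below 45, what ends an episode, and whether the 60 minutes runs from the start or the end of the prior one. Apply the rule identically to all stored traces. Report the primary count under one-, two- and three-reading rules side by side, and disclose that the rule was set after the traces had been reviewed. Separately, reconcile the SUMMARY with MONITORING FOR HYPOGLYCEMIA on which sensor lows receive a blood test.

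The cost is SAP wording and a recount; no new data are needed. True lows shorter than the minimum run leave the main count, and the headline number falls. Artefacts that persist, such as drift or pressure on the sensor, are not removed: under all-drift error about one false event per infant-day remains at glucose 55 even with three readings.

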Maternal data, including mother's age, pregnancy history, type of diabetes, and treatment of diabetes during pregnancy were collected. Neonatal characteristics collected included sex, race, ethnicity, gestational age, birth weight, type of delivery, and other risk factors for hypoglycemia. Perinatal stressors were defined as an Apgar score <7, admission to NICU, or treatment of the infant beyond the usual suctioning and stimulating that routinely occurs after birth.¹⁴ Prematurity was defined as birth at <37 weeks gestation. Small for gestational age (SGA) infants weighed less than the 10th percentile for gestational age, whereas large for gestational age (LGA) infants weighed greater than the 90th percentile for gestational age.

Power calculation

Using an older retrospective CGM device in a similar cohort of at-risk infants, Harris found that using similar SOC intermittent heel-stick glucose monitoring, 32% of infants had glucose levels <47 mg/dL.¹⁵ We estimated that in our cohort, the SOC would find 32% of these high-risk infants with glucose levels <47 mg/dL. We estimated that with a sample size of 40, we should be able to detect a higher CGM rate of hypoglycemia of *57% (80% power, alpha = 0.05, one sided). However, because we were unable to recruit 40 infants during the time frame of the randomized trial, we modified the study design; instead, our goal was to determine if there was additional benefit of using CGM monitoring to detect hypoglycemia missed by SOC testing and to determine the false-positive rate of CGM alerts for hypoglycemia.

Outcome measures

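### CGM error size is summarised only by one MARD pooled over glucometer pairs, with 'low' CGM readings left out, so it says little about error below 45 mg/dL

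*Combined protocol and SAP*

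**What the plan says.** The SUMMARY sets out to evaluate "the utility of CGM systems to detect clinically significant hypoglycemia in infants". Under DATA ANALYSIS, Outcome measures, the threshold is fixed: "Hypoglycemia was defined as a glucose concentration of <45mg/dL".

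The same section defines the accuracy statistic: "The mean absolute relative difference (MARD) was calculated by taking the absolute value of the difference between the CGM and hospital glucometer values", followed by "dividing by the hospital glucometer value individually, and then taking the mean of these values". No glucose bands, error in mg/dL or numbers of pairs are specified.

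Just before that definition, the section says how CGM readings displayed as 'low' are handled. They count as 39 mg/dL when an infant's average CGM glucose is computed, but they "were excluded from the accuracy analysis".

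MARD is not named as a primary or secondary outcome. The primary outcome is a count of sensor-detected events that standard care missed. For the rest: "Secondary outcome measures were sensitivity, specificity, and positive predictive value of the device to detect hypoglycemia".

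**The concern.** MARD is the only planned measure of how large the sensor's error is. The alerts and the primary count depend on readings around 45 mg/dL, whereas a pooled mean is governed by whichever glucose range supplies most pairs. If most pairs are in the normal range, a reassuring MARD can coexist with poor accuracy where the trial needs it.

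The exclusion adds a second problem. A 'low' display is most likely when glucose is low or when the sensor reads falsely low. Dropping those pairs thins out the low range and does so selectively, according to the sensor's own error. What is at stake is a reader taking the reported MARD as evidence of accuracy in hypoglycemia.

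**Working it through.** **No planned figure to reproduce.** The documents give no observed or expected MARD, no number of pairs and no share of pairs below 45 mg/dL. The nearest figure, in Power calculation, is "32% of infants had glucose levels <47 mg/dL". That is a rate per infant, at a different cut-off, from an earlier study. The share therefore has to be assumed and varied.

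**1. Dilution by arithmetic.** Let f be the share of retained pairs with glucometer <45 mg/dL. Then

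pooled MARD = (1 − f) × MARD at ≥45 + f × MARD at <45.

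| f | ≥45: 10%; <45 rises 10% → 40% | ≥45: 15%; <45 rises 15% → 40% |
|---|---|---|
| 5% | 10% → 11.5% | 15% → 16.25% |
| 10% | 10% → 13% | 15% → 17.5% |
| 20% | 10% → 16% | 15% → 20% |
| 30% | 10% → 19% | 15% → 22.5% |

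A worsening of 25 to 30 points in the low range appears as 1.25 to 1.5 points at f = 5%, and as 7.5 to 9 points at f = 30%.

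**2. Simulation without the exclusion.** Assumed inputs: reference glucose normal, mean 65, SD 15 mg/dL (8.8% of pairs <45); unbiased sensor error, SD 8 mg/dL.
- MARD is 10.4% overall, 16.8% for pairs <45 and 8.8% for pairs ≥60.
- With the error SD doubled only below 45, low-range MARD is 33.5% and overall MARD is 11.9%.
- Check by the identity: 0.088 × (33.5 − 16.8) = 1.5 points, and 10.4 + 1.5 = 11.9.

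**3. The same simulation with the plan's exclusion.** 'Low' is taken as a sensor reading below 40 mg/dL. This is inferred from the 39 mg/dL substitution and is not stated in the plan.
- About 54% of pairs with reference <45 drop out, and the low share of retained pairs falls from 8.8% to 4.3%.
- Pooled MARD is 9.7%, and 10.5% with the low-range error doubled: a shift of 0.8 points instead of 1.5.
- With error SD 6 to 10 and glucose mean/SD of 65/15 or 60/12, about 51–55% of low pairs are lost, and the shift is no more than about 1.2 points.

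**4. What the retained low pairs show** (65/15, error SD 8).
- Unbiased sensor: retained pairs <45 have a mean error of +6.0 mg/dL although the true mean error is 0, because the pairs that read downwards were removed.
- Sensor reading 15 mg/dL too low whenever reference is <45: MARD over all low pairs is about 40%. Only about 4% of those pairs are retained, and their MARD is about 7%.

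**5. Direction of error, under a second model** (lognormal reference, log SD 0.25, sensor CV 12.5%, 10% of pairs <45 before exclusion, readings below 40 dropped).

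| Bias when reference <45 | Pooled MARD | Sensitivity, all pairs |
|---|---|---|
| none | 9.7% | 77% |
| +15 mg/dL | 12.5% | 6% |
| +20 mg/dL | 13.8% | 1% |
| −15 mg/dL | 9.8% | about 100% |

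Upward bias shows clearly in sensitivity. Downward bias shows in neither column: about 99% of the low pairs are dropped from MARD, and every true low is still classified as low.

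**The case against.** The strongest reply is that the plan does not rely on MARD to judge detection. Sensitivity, specificity and PPV are the named secondary outcomes, and Power calculation adds the false-positive rate of alerts to the goals. A sensor reading 15–20 mg/dL too high at low glucose would be exposed by sensitivity falling from 77% to 1–6%. No decision rule uses MARD, and EVALUATION AND TREATMENT OF HYPOGLYCEMIA ties treatment to glucometer values only. All of this stands, and it limits the importance of the point.

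It does not remove the point. Classification at one cut-off ignores the size of the error: with a true value of 42 mg/dL, readings of 46 and 70 are both misses, although the errors are 4 and 28 mg/dL. The text also leaves unclear whether the 'low' exclusion extends to sensitivity, specificity and PPV.

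A reader might infer that about nine-tenths of pairs lie above 45 mg/dL and that MARD therefore barely responds to low-range error. The documents support neither statement. The share is not given, and bedside tests prompted by alerts below 46 mg/dL (MONITORING FOR HYPOGLYCEMIA) could raise it, while the exclusion lowers it. In the second model, with 30% of pairs low before exclusion, a +15 mg/dL bias moves pooled MARD from 9.5% to 18.6%, which is plainly visible.

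A reader might also worry that MARD will differ between groups merely through the mix of glucose values. Relative error does depend on that mix (15 mg/dL is 37.5% at 40 mg/dL and 18.8% at 80 mg/dL), but no comparison of MARD between groups is planned.

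**Conclusion.** The point holds in a limited form. The plan's only measure of error size is diluted in the range the trial is about, and the 'low' exclusion removes many of the most relevant pairs. In the illustration about half of the truly low pairs are lost, and doubling the low-range error moves pooled MARD from 9.7% to 10.5%. These figures rest on assumed glucose and error distributions and on 'low' meaning below 40 mg/dL. With a larger share of low pairs and upward error, the dilution is much weaker.

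It does not follow that the trial cannot assess detection of hypoglycemia, or that its main conclusions depend on MARD. The weakness lies in what may be claimed about the size of the error at low glucose. Splitting MARD by band without accounting for the excluded readings would not cure it, because the retained pairs below 45 mg/dL can themselves look falsely accurate (about 7% against a true 40% under the −15 mg/dL bias).

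**What to change.** - Keep overall MARD. Add the mean absolute difference in mg/dL and MARD by glucometer band (<45, 45–59, ≥60 mg/dL), with the number of pairs in each band.
- For each band, report how many pairs were excluded because the CGM read 'low', and give their glucometer values.
- Add a sensitivity analysis that includes those pairs at the 39 mg/dL the plan already uses for average glucose. This limits downward error: a glucometer value of 44 gives (44 − 39)/44 = 11.4% however far below 39 the sensor actually was. It therefore supplements the counts and does not replace them.
- State what sensor value 'low' represents, and state that sensitivity, specificity and PPV count 'low' readings as CGM-positive.
- Do not base accuracy claims for hypoglycemia on pooled MARD, or on the retained <45 mg/dL pairs alone.

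The cost is some SAP wording and one extra table from pairs already collected. The lowest band will probably hold few pairs and have wide intervals, which fairly shows how little evidence there is in that range.
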